#### Handling of missing data:

Every effort will be made to collect complete data on each study day. With respect to safety evaluation, it is not planned to impute missing data.

## 3. HUMAN SUBJECTS

### 3.1 SUBJECT POPULATION

The racial, gender and ethnic characteristics of the proposed subject population in this research protocol shall reflect the demographics of the population of Pittsburgh and the surrounding area. We shall attempt to recruit subjects in proportion to these demographics. No exclusion criteria shall be based on race, ethnicity or gender.

Every effort will be made to keep subjects in the study until they complete all study procedures.

#### 3.1.1 Inclusion of Women and Minority

Both men and women of all races and ethnic groups are eligible for this trial. Women who meet the inclusion criteria, and have none of the exclusion criteria, will be enrolled without restriction as dictated by the study protocols. Because of the use of a study medication, woman of child bearing potential must meet specialized inclusion/exclusion criteria to minimize this risk.

#### 3.1.2 Inclusion of Children

Children under the age of 18 will not be recruited for this protocol because of the need to explore potential adverse effects of the study treatment more fully in adults. .

### 3.2 INCLUSION CRITERIA

Potential study subjects must satisfy the following criteria to be enrolled in the study

#### WHO Group I PAH (n = 20)

Diagnosis of RHC confirmed WHO Group I PAH in any of the following categories:

- Idiopathic, primary or familial pulmonary arterial hypertension (IPAH, PPH, or FPAH)

**OR**

- PAH associated with one of the following connective tissue diseases:
  - i. Systemic sclerosis (scleroderma)
  - ii. Limited scleroderma
  - iii. Mixed connective tissue disease
  - iv. Systemic lupus erythematosus
  - v. Overlap syndrome;

**OR**

- PAH associated with:
  - i. Human immunodeficiency virus (HIV) infection;
  - ii. Simple, congenital systemic-to-pulmonary shunts at least one year post-surgical repair.
  - iii. Exposure to legal drugs, chemicals and toxins, such as fenfluramine, derivatives, other anorexigens, toxic rapeseed oil or L-tryptophan. Subjects with PAH associated with illegal drug use, such as methamphetamine excluded.

Stable PAH for at least 3 months if on therapy

#### WHO Group II (n=20)

- Pulmonary capillary wedge pressure (PWCP) > 15

AND

- Transpulmonary Gradient (TPG) > 12

#### WHO Group III PH (n = 10)

Has WHO functional class II-IV symptoms

Had the diagnosis of PH confirmed by a cardiac catheterization with the following values:

- Mean pulmonary artery pressure (mPAP)  $\geq$  25 mm Hg (at rest);
- Pulmonary capillary wedge pressure (PCWP) or left ventricular-end diastolic pressure  $\leq$  15 mm Hg (if diagnosed with PAH); and
- Pulmonary vascular resistance (PVR)  $\geq$  3 mm Hg/L/min or  $\geq$  240 dynes\*sec/cm^5;

#### WHO Group I, II and III

Age 18 and older;

Able and willing to participate in right heart catheterization;

Evidence of a personally signed and dated informed consent document indicating that the subject has been informed of all pertinent aspects of the study;

Subjects who are willing and able to comply with scheduled visits, treatment plan, laboratory tests, and other study procedures;

### **3.3 EXCLUSION CRITERIA**

Subjects meeting any of the exclusion criteria at baseline will be excluded from participating in study.

- Age less than 18 years;
- Baseline systemic hypotension, defined as MAP less than 50 mmHg;
- Required intravenous inotropes within 30 days prior to study participation;
- Has uncontrolled systemic hypertension as evidenced by sitting systolic blood pressure >160 mm Hg or sitting diastolic blood pressure >100 mm Hg at Screening;
- Has a history of portal hypertension or chronic liver disease, including hepatitis B and/or hepatitis C (with evidence of recent infection and/or active virus replication) defined as moderate to severe hepatic impairment (Child-Pugh Class B-C);
- Has chronic renal insufficiency as defined by serum creatinine >2.5 mg/dL at Screening or requires dialytic support;
- Has a hemoglobin concentration <9 g/dL at Screening;
- History of atrial septostomy within 6 months prior to Day 1 visit;
- Repaired or unrepaired congenital heart disease (CHD);
- Pericardial constriction;
- Confirmed diagnosis of restrictive or constrictive cardiomyopathy;
- Left ventricular ejection fraction <40% by multiple gated acquisition scan (MUGA), angiography or echocardiography;
- Symptomatic coronary disease with demonstrable ischemia;
- Other severe acute or chronic medical or laboratory abnormality that may increase the risk associated with study participation or investigational product administration or may interfere with the interpretation of study results and, in the judgment of the investigator, would make the subject inappropriate for entry into this study;
- Has a psychiatric, addictive or other disorder that compromises the ability to give informed consent for participating in this study. This includes subjects with a recent history of abusing alcohol or illicit drugs 30 days prior to study screening Day 0 and for the duration of the study;

- Poorly controlled asthma defined by active wheezing and/or cough with FEV1 < 70% predicted, responsive to inhaled BD (>15% increase in FEV1 with BD);
- Investigators, study staff or their immediate families;
- Clinically significant intercurrent illness (including lower respiratory tract infection) or clinically significant surgery within 4 weeks before the administration of study drug;
- Personal or family history of congenital or acquired methemoglobinemia;
- Personal or family history of RBC CYP B5 reductase deficiency;
- Known or suspected hypersensitivity or allergic reaction to sodium nitrite;
- Personal history of glucose-6-phosphate dehydrogenase (G6PD) deficiency or any contraindication to receiving methylene blue;
- If female, is pregnant or breast feeding, or has a positive pregnancy test result predose;
- Receipt of an investigational product or device, or participation in a drug research study within a period of 15 days (or 5 half-lives of the drug, whichever is longer) before the first dose of study drug;
- Blood loss or blood donation >550 mL within 90 days or plasma donation >500 mL within 14 days before administration of study drug;
- RHC < 2 weeks from treatment visit unless clinically indicated

## **4. RECRUITMENT AND INFORMED CONSENT PROCEDURES**

### **4.1 RECRUITMENT METHODS**

The potential study subjects will be recruited from the UPMC Heart and Vascular (HVI) and Comprehensive Lung Center (CLC) or inpatients at UPMC Presbyterian Hospital. Potential subjects will be first identified or referred to the investigator who may also be the primary care or treating physician. The investigator who may already have knowledge of and access to subjects' information may review the subjects' records to identify potential research subjects for the study. After identifying potentially eligible subjects, the investigator will then approach these subjects to discuss the research opportunity.

To minimize the possibility that subjects will feel obligated to participate, investigators will reinforce with their subjects that participation is voluntary, that they do not have to participate, and the decision not to participate will not affect their care, now or in the future. The investigator will also allow subjects to make further inquiries if they are interested.

### **4.2 INFORMED CONSENT PROCEDURES**

Informed consent is a process that is initiated prior to the individual's agreeing to participate in the study and continuing throughout the individual's study participation. Extensive discussion of risks and possible benefits of participation in this study will be provided to the subjects and their families. Consent forms describing in detail the study procedures and risks are given to the subject and written documentation of informed consent is required prior to enrolling in the study. Consent forms will be IRB approved and the subject will be asked to read and review the document. Upon reviewing the document, the investigator will explain the research study to the subject and answer any questions that may arise. The subjects will sign the informed consent document prior to being enrolled in the study. The subjects should have the opportunity to discuss the study with their surrogates or think about it prior to agreeing to participate. The subjects may withdraw consent at any time throughout the course of the study. A copy of the informed consent document will be given to the subjects for their records. The rights and welfare of the subjects

will be protected by emphasizing to them that the quality of their medical care will not be adversely affected if they decline to participate in this study.

Prior to performing any of the research study procedures or interventions, subjects must provide informed consent. The investigator will verbally explain the study to the potential subject in a language understandable to subjects, providing all pertinent information (purpose, procedures, risks, benefits, alternatives to participation, etc.), and will allow potential subjects ample opportunity to ask questions to elicit a better understanding of the study. Following this verbal explanation, potential subjects will be provided with a local IRB approved consent form and will be asked to read and review the document. Upon reviewing the document, the investigator will provide adequate opportunity for the subject to consider all options, answer any additional questions the potential subject may have. Every effort will be made to ensure that subjects have comprehended the study information prior to obtaining subject's voluntary agreement to participate.

In addition, older potential participants whose competency to consent is in question will be tested for sufficient comprehension and recall of the information presented. Prospective subjects who do not remember the important facts about participation in the research study after repeated testing will not be included in the study. The investigators will also assess whether a participant understands experimental procedures over time, including assessment throughout the full duration of participation in the study.

The subjects may withdraw consent at any time throughout the course of the study. A copy of the informed consent document will be given to the subjects for their records. The rights and welfare of the subjects will be protected by emphasizing to them that the quality of their medical care will not be adversely affected if they decline to participate in this study.

## **5. POTENTIAL RISKS AND BENEFITS**

### **5.1 POTENTIAL RISKS**

As with any experimental procedure, there may be adverse events or side effects that are currently unknown, and certain of these unknown risks could be permanent, severe or life threatening. Every attempt will be taken to minimize these risks.

#### Risks of Sodium Nitrite Inhalation Solution:

The first-in-man clinical study of AIR001 Inhalation Solution, Study AIR001-CS01, was a dose escalation study designed to identify the dose limiting toxicity, the maximum tolerated dose, and the pharmacokinetics of AIR001 administered. The most important safety finding was a decline in systolic and diastolic blood pressure at the highest dose tested, 176 mg. Dose-dependent asymptomatic increases in heart rate were noted at all doses, although at doses up to and including the maximum tolerated dose of 125 mg, the heart rate changes were well tolerated. Increase in heart rate was not always associated with a change in blood pressure. Significant levels of methemoglobin, or changes in pulmonary function, were not observed. Methemoglobin levels increased at the highest doses administered, but remained less than 3.5% in all subjects.

As with any drug product administered via inhalation, it is possible that susceptible individuals, such as those with unrecognized asthma, will develop bronchospasm upon exposure to inhaled sodium nitrite solution. There were no changes in pulmonary function noted in AIR001-CS01, which excluded subjects with asthma or abnormal baseline pulmonary function tests.

In Study AIR001-CS02, inhaled nitrite was generally well tolerated under hypoxic conditions at doses up to and including 113 mg. Additionally, a sustained reduction in hypoxia-induced pulmonary hypertension was demonstrated, suggesting that safely delivered doses of AIR001 Inhalation Solution B result in clinically significant vasodilatation, presumably through a mechanism of intrapulmonary reduction of nitrite to NO.

In this study, the significant treatment related adverse event was a decrease in blood pressure. The magnitude of the change in blood pressure from the hypoxic baseline was less than from the normoxic baseline, suggesting that hypoxia itself has an effect on BP.

#### Risks of Nitric Oxide Inhalation:

The inhalation of NO is usually well tolerated without side effects.

Infrequent risks: decrease pulmonary vascular tone, but because of its short biological half-life will be metabolized or inactivated before reaching the systemic circulation. Other risks: Massive overdoses of nitric oxide are fatal (from 500-1000ppm).

#### Risks of Sildenafil/Tadalafil (PDE-5 Inhibitor):

These medications are commonly used and FDA approved to treat Pulmonary Hypertension. These medications may lower blood pressure significantly if taken together with some other medications like nitroglycerin. AIR001 may cause similar effects in this study in combination with PDE-5I.

Subjects will be closely monitored throughout the entire procedure and should blood pressure drop significantly with the first inhaled dose of AIR001, study participant will not receive the next higher dose.

#### Risks of Blood Drawing:

The amount of blood to be drawn over the course of this research study could be a maximum of 5 tablespoons. To minimize the risks of blood tests, a licensed technician or registered nurse will draw your blood.

Common risks include temporary discomfort, bruising which may last for several days, redness, swelling, lower hemoglobin level. Infrequent risks include a subject may feel lightheaded or faint when blood is drawn. This is usually due to nervousness and is not usually serious. Rare risks include infection, and bleeding.

#### Risks of Echocardiography:

This is a noninvasive procedure. There is no known risk associated with this procedure.

#### Risks of Right heart Catheterization:

Common risks: pain at the needle entry site and slight risk of bleeding around the site. bruising at site, lightheadedness or dizziness during the needle stick.

Infrequent risks: puncturing the lung which would require a chest tube insertion, irregular heartbeats which usually stop when the long tube is removed from the heart.

Very rare complications include cardiac arrhythmias, cardiac tamponade, low blood pressure, infection, or embolism caused by blood clots at the tip of the catheter.

#### Risks of the Use of Micromanometer Catheter during Catheterization:

The micromanometer pressure and flow catheter are FDA approved, and have been used for clinical/investigative indications for over 25 years. Moreover, these catheters do not pose any inherent risk to patients. The catheter will be placed through the clinical Swann-Ganz catheter that is within the preexisting jugular venous sheath. This obviates the need for an additional

venipuncture. This catheter has successfully been used without complications by the study Principal Investigator for the past 5+ years.

#### Risks of Medications used during Catheterization:

The medications used for sedation are relatively brief in duration and should wear off within several hours. The side effects are listed below for each drug.

1 % Lidocaine: will be used to numb the area prior to the insertion of the cardiac catheter into either your neck or groin vein. A common side effect is slight burning at the site which dissipates quickly.

Fentanyl: Common side effects include temporary light-headedness, dizziness, nausea, vomiting or sweating.

Midazolam: Common side effect includes drowsiness. Infrequent side effects are nausea, vomiting. Breathing problems are rare.

Allergic reactions (e.g., hives, itching, etc.) to lidocaine, fentanyl, or midazolam are rare.

#### Risks of Chest X-Ray during the Catheterization

A chest x-ray may be done, if clinically indicated, on participants that a neck vein is used for the catheterization. A chest X-ray performed for the purpose of this research study involves exposure to radiation. Each chest X-ray will result in a radiation dose of approximately 0.03 rem to the chest with minimal exposure of other body areas. For comparison, radiation workers are permitted, by Federal regulation, to receive a maximum annual radiation dose of 20 rems to the most sensitive organs of their body. There is no minimum amount of radiation exposure that is recognized as being totally free of the risk of causing genetic mutations (abnormal cells) or cancer. However, the risk associated with the amount of radiation exposure received from participation in this study is considered to be low and comparable to everyday risks.

#### Reproductive Risks:

It is not known if the study drug can affect an unborn baby. Therefore, subjects should not become pregnant or father a baby while on this study. If subjects are physically able to father a baby, subjects must use an effective method of birth control while on this study. If subjects become aware that they or their sexual partner is pregnant during the course of their participation in this research study, subjects must contact, as soon as possible, the study investigator.

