	
recent history of abusing alcohol or illicit drugs 30 days prior to study screening Day 0 and for the duration of the study;
 

• Poorly controlled asthma defined by active wheezing and/or cough with FEV1 < 70% predicted, responsive to inhaled BD (>15% increase in FEV1 with BD);

• Investigators, study staff or their immediate families;

• Clinically significant intercurrent illness (including lower respiratory tract infection) or clinically significant surgery within 4 weeks before the administration of study drug;

• Personal or family history of congenital or acquired methemoglobinemia;

• Personal history of RBC CYP B5 reductase deficiency;

• Known or suspected hypersensitivity or allergic reaction to sodium nitrite;

• Personal history of glucose-6-phosphate dehydrogenase (G6PD) deficiency or any contraindication to receiving methylene blue;

• If female, is pregnant or breast feeding, or has a positive urine or blood pregnancy test result predose;

• Receipt of an investigational product or device, or participation in a drug research study within a period of 15 days (or 5 half-lives of the drug, whichever is longer) before the first dose of study drug;

• Blood loss or blood donation >550 mL within 90 days or plasma donation >500 mL within 14 days before administration of study drug;

• RHC < 2 weeks from treatment visit unless clinically indicated

Study Endpoints:	
Primary endpoint: The primary outcome measures for this study is change in pulmonary vascular resistance measured by right heart catheterization from time zero compared with peak effect within 60 minutes post completion of nebulized dose of nitrite.
 
Secondary endpoints: The secondary endpoints measure:
 

• Time to maximum PVR decrease;

• Repeated measures ANOVA (RM-ANOVA) for change in PVR calculated from the start of inhalation and at times 15, 30, 45 and 60 minutes post end of nebulization.

• Change in mean pulmonary artery pressure, transpulmonary gradient and cardiac output (CO)/cardiac index (CI),

• Change in systemic blood pressure,

• Change in SVR, RV systolic (dP/dtmax/IP, PWRmax/EDV, RV EF, TAPSE), RV diastolic function (dP/dtmin, Tau),

- Change in pulmonary vascular impedance / Wave Intensity,

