### Screening

- Medical history review and demographics
- Complete history and physical examination to include vital signs, blood pressure, body weight, and height.
- Assessment of oxygen saturation
- Baseline clinical laboratory evaluations including complete blood count with differential, platelets, electrolytes, glucose, BUN, serum creatinine, liver function tests, PT/PTT, nt-ProBNP..
- Urine pregnancy test for female of childbearing potential.
- Informed, written consent may be obtained after subject meets eligibility criteria or on day of Study visit (Day 1)

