## 2.11. SCHEDULE OF ACTIVITIES (STUDY ASSESSMENT TABLE)

The table below summarizes the protocol procedures that will be performed at screening, during the study treatment, and at follow-up.

Study Phase	Screening	Pre-Treatment	Treatment				Post-Treatment Follow-Up Monitoring	
Visit Type	Outpatient Clinic	Outpatient Cath Lab				Phone Assessment	Outpatient Clinic	
Days on Intervention	Day 0	Day 1				Day 3	Day 30	
Study Procedures		Baseline	Dose 1	Dose 2	Final Measurement			
Informed Consent	X							
Medical History and Demographics	X							
I/E Criteria	X							
Physical Exam	X	X					X	
Vital Signs	X	X					X	
Oxygen Saturation	X	X	X	X	X		X	
Laboratory Tests***	X	X					X	
Urine Pregnancy Test Δ	X	X						
Non-invasive blood pressure measurement		X	X	X				
Right Heart Catheterization (RHC): RA, RV, PA, PCWP, CO/CI (RV measurements at baseline, pre-dose and 60minute interval post last dose AIR001)		X	X	X	X			
Micromanometry		X			X			
Echocardiogram		X			X			
Inhaled NO at 40 ppm if PCWP < 25		X						
PK Sampling*		X	X	X				
metHgb Level§		X	X	X	X			
Plasma cGMP		X	X	X				
Platelet Mitochondrial Analysis		X	X	X				
AE Assessment	X	X	X	X	X	X	X	
Interval History Assessment						X		

Δ Urine pregnancy test will be performed only on female of childbearing potential.

\*\*\* Clinical laboratory tests may be repeated on study visit 1 if screen lab results deemed clinically significant and warrant repeat testing or inadvertently not collected at screen visit.

\* PK Sampling for Nitrite: Blood samples will be obtained at pre-dose and at the end of nebulization at the presumed peak nitrite concentration for each tolerated dosage time points; 15 minutes post inhalation.

§ Methemoglobin (metHgb) levels: will be measured at the following time points: pre-dose, 5, 15, 30 and 60 minutes each dose of AIR001 and at 120 minutes post last dose of AIR001.

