#### **2.12.6. Laboratory Testing**

Peripheral blood samples will be evaluated for baseline and follow-up comparison purposes which include complete blood count with differential, platelets, electrolytes, glucose, BUN, serum creatinine, liver function tests, PT/PTT, and nt-ProBNP. Urine pregnancy test may be performed only on female of child-bearing potential on Day 0 and Day 1.

Screening lab samples may be collected and analyzed at UPMC laboratories or at outlying facility of subject's choice. Lab results will be added to research chart for comparison. All 30-day samples will be analyzed at UPMC Presbyterian laboratory with the exception of the ntPro-BNP which may be processed and analyzed through the Pulmonary, Allergy and Critical Care Medicine (PACCM) research lab.

Baseline laboratory results within 6 months of screen visit may be used as baseline comparison and will not be repeated for research purposes. Blood samples may be collected on study visit 1 if baseline screening results are deemed clinically significant and warrant repeat testing or inadvertently not collected at screen visit.

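### Fetal risk is called unknown, yet the only mandatory contraception rule covers subjects who can father a child; none covers women who could conceive, and the Day 1 pregnancy test is not firmly required throughout

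*Combined protocol and SAP*

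**What the plan says.** **Contraception.** Section 5.1 (Reproductive Risks) states that fetal risk is unknown and asks subjects in general neither to conceive nor to father a child. The mandatory sentence that follows is limited to one group: "If subjects are physically able to father a baby, subjects must use an effective method of birth control while on this study". The section then asks for notification: "If subjects become aware that they or their sexual partner is pregnant during the course of their participation in this research study", they are to contact the investigator promptly.

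**Eligibility.** Section 3.1.1 says that, because a study drug is used, "woman of child bearing potential must meet specialized inclusion/exclusion criteria to minimize this risk". The criterion specific to women is an exclusion. The Synopsis words it as "If female, is pregnant or breast feeding, or has a positive urine or blood pregnancy test result predose" and section 3.3 as "If female, is pregnant or breast feeding, or has a positive pregnancy test result predose". The inclusion criteria common to all three WHO groups (Synopsis and section 3.2) do not mention contraception.

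**Testing.** The schedule in section 2.11 marks a urine pregnancy test at screening and at the Day 1 baseline, with the footnote "Urine pregnancy test will be performed only on female of childbearing potential". Section 2.12.6 says "Urine pregnancy test may be performed only on female of child-bearing potential on Day 0 and Day 1".

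**The concern.** If fetal risk is unknown, the subjects who matter most are women who could be pregnant when they inhale the drug. The protocol makes contraception mandatory for the other group. A site that follows the text exactly could enrol and dose a woman of childbearing potential who uses no contraception, provided her pre-dose test is negative. A very early pregnancy may not show on that test, so contraception already in use before dosing is the measure that bears on it.

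The test is the main remaining safeguard, and the sections do not describe it with equal firmness. At stake is a small, avoidable safety risk to a few subjects. Nothing in the efficacy analysis depends on it.

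**Working it through.** No arithmetic applies. The check sets the relevant sections side by side.

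**1. Who must use contraception?**
- Section 5.1: subjects able to father a child must. All subjects are told that they should not conceive or father a child.
- Synopsis inclusion criteria and section 3.2: nothing on contraception.
- Synopsis exclusion criteria and section 3.3: pregnancy, breast feeding or a positive pre-dose test excludes; nothing on contraception.

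No other section supplies a rule for women.

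**2. Which exposure is left open?** The Synopsis gives treatment as one day: 45 mg, then 90 mg about 60 minutes later if tolerated. A known pregnancy or a positive pre-dose test excludes. The remaining case is mainly conception shortly before Day 1, too recent for the test to show.

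**3. Would extending the section 5.1 sentence close that case?** Not alone. The sentence applies while the subject is on the study. The screening list in section 2.10.1 allows written consent as late as Day 1, so an on-study duty may begin only on the dosing day. An eligibility criterion that asks about contraception already in use at enrolment does reach back before dosing. Both changes are needed: the first removes the asymmetry, the second addresses the residual exposure.

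**4. How firm is the Day 1 test?**

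| Section | Status of the test |
|---|---|
| 2.11, schedule and footnote | Marked at Day 1 baseline; *will* be performed |
| 2.12.6 | *May* be performed, Day 0 and Day 1 |
| 2.10.2, pre-dose baseline list | Not listed |
| 2.10.1, screening | Tests done in the 6 months before screening are not repeated; no exception for the pregnancy test |

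The schedule is firm, but the procedural text is weaker. Read literally, the 6-month rule lets an old negative result stand as the screening test, so the Day 1 test carries the weight. It is the one left permissive in section 2.12.6 and absent from the working list in section 2.10.2.

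**5. What happens after a pregnancy is reported?**
- Section 2.14 lists pregnancy as a reason for which a subject may be withdrawn.
- Section 5.5.5.2 (Abnormal test findings) makes a test finding that leads to discontinuation an adverse event.
- Section 5.5.2 follows adverse events past the observation period, but lets the Principal Investigator end follow-up.
- Section 2.10.4 follows clinically significant findings from the final assessments. No pregnancy test is scheduled at that visit.
- Section 5.5.5.1 counts a birth defect as a serious adverse event.

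Together these give a partial, implicit route for a subject's own pregnancy. None names pregnancy outcome, and a partner's pregnancy is not a subject's test finding.

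**6. Are women of childbearing potential likely to be enrolled?** Section 1.3.1 gives a female-to-male ratio of 2.3:1 and a median age at diagnosis of 36 for PAH, and 20 of the 50 planned subjects are Group I. These are disease-level figures. They make enrolment of such women plausible but do not give a number.

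**The case against.** The strongest reply is that the window is narrow and largely covered. Exposure is confined to one day, pregnancy and breast feeding exclude, a test is scheduled on the day, and everyone is told not to conceive and to report a pregnancy. The exclusion of a positive pre-dose result presupposes a test, and section 2.12.6 can be read as limiting *who* is tested rather than making testing optional. All of this stands. It is why the point is minor and why the testing change is mostly a matter of consistent wording.

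Three stronger readings are tempting, and the documents do not support them.

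- *A reader might infer that section 3.1.1 makes a promise that the criteria break.* It promises criteria specific to women of childbearing potential, and one exists. It does not promise a contraception criterion. The promise is thinly met, not broken.
- *A reader might infer that pregnancies are lost to follow-up.* The route in step 5 covers part of this for subjects. What is missing is explicit wording, and partners. The months between the last scheduled contact and a birth do not measure harm either, and no section describes fetal exposure through a father or from conception after dosing.
- *A reader might infer that women receive no contraception instruction at all.* Section 4.2 says the consent form describes procedures and risks in detail, and those pages were not available. They may contain one. The eligibility lists would still be silent.

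**Conclusion.** The point holds as a minor safety and conduct gap. The one mandatory contraception sentence omits subjects who could conceive, no eligibility criterion makes up for it, and the Day 1 pregnancy test is firm in the schedule but not in the text that staff would follow. The residual risk is small. It rests on the judgement that a pre-dose test can miss a very early pregnancy. The documents give no number of women of childbearing potential and no rate, so no count is claimed. Follow-up of reported pregnancies is a secondary wording matter. The sample size, the primary PVR endpoint and its analysis are unaffected.

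**What to change.** 1. **Contraception.** In section 5.1, extend the mandatory sentence to subjects able to conceive. In both eligibility lists (Synopsis; sections 3.2 and 3.3), require that women of childbearing potential are using effective contraception at enrolment, checked by history.
2. **Day 1 test.** In section 2.12.6, change *may* to *will*. Add the test to the pre-dose baseline list in section 2.10.2, and exempt it from the 6-month no-repeat rule in section 2.10.1. This brings the text into line with section 2.11.
3. **Pregnancy outcome (secondary).** State that any reported subject pregnancy, and any partner pregnancy with the partner's agreement, is followed by telephone to its outcome. A birth defect would then be handled under the existing serious adverse event definition and reported where the criteria in section 5.5.6.1 are met.

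The cost is protocol and consent wording, one history question and a rare telephone contact. The schedule already includes the test. Because consent may be given on Day 1, the history can check only current use, so a few women may prove ineligible or decline on the day. A partner may refuse follow-up.
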